We will specifically exclude pediatric ankle fractures in children under 18 years-of-age, tibial plafond (pilon) fractures in children and adults, medial malleolar osteotomies to access the talus, perform an ankle fusion, or deal with a pathologic lesion, osteonecrosis, or infection due to their diversity in diagnosis, management, and weight bearing status. Patients with prior surgical treatment of the ankle for fracture, deformity, infection, neoplasia, or other pathologic process on the ipsilateral extremity will also be excluded.

Patients that are non-weight bearing on one or both lower extremities prior to sustaining their ankle injury will be excluded.

Randomization

All elective and emergent admissions to Stanford Hospital and Clinics and Kaiser Permanente – South Sacramento that meet our inclusion/exclusion criteria will be identified and solicited for consent. Patients will be randomized by sealed envelope to surgical fixation with traditional headed screws, plates, and wires or Acutrak headless compression screws. At the time of randomization, the fracture pattern and severity, past medical history and medications, and demographic data will be documented.

Follow-up Protocol

After operative fixation, patients will receive fracture follow-up with a clinical evaluation for tenderness, radiographs to evaluate stability and union at 2 weeks, 6 weeks, 3 months of surgery and complete the PROMIS and VAS pain scores. Patients will be followed by telephonically once the fracture union is confirmed radiologically by the operating surgeon at 6 months, 1 year, and 2 years after surgical fixation. The VAS pain scores will be administered telephonically and the PROMIS questionnaires will be mailed to the patients (Table 1).⁹

Table 1: Protocol Summary

Time and Event Table	Injury/Office	2 weeks	6 weeks	3 months	6 months (over Telephone & mail)	1 year (over Telephone & mail)	2 years (over Telephone & mail)
Discuss Study	X						
Screening Log	X						
Informed Consent	X						
Eligibility Worksheet	X						
Demographic Data	X						
Medical History	X						
Randomization	X						
Clinical Assessment							
•Medial Ankle Tenderness	X	X	X	X	X	X	X
•Lateral Ankle Tenderness	X	X	X	X	X	X	X
Patient Reported Outcomes							
•PROMIS Score	X	X	X	X	X	X	X
•VAS Pain (by location)	X	X	X	X	X	X	X
•On Narcotics (yes/no)	X	X	X	X	X	X	X
Radiographs							
•Anterior-to-Posterior Ankle	X	X	X	X	-	-	-
•Lateral Ankle	X	X	X	X	-	-	-
Operative/Device	X						

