Removal of Hardware		X	X	X	X	X	X
Adverse Event	X	X	X	X	X	X	X
End of Study							X

Criteria for Removal of Hardware

Hardware may be removed if there is a surgical indication or patient/surgeon preference for removal. Patients will be asked whether they feel bothersome sensitivity at the both medial and lateral malleolus. If they mention sensitivity to light touch that is not bothersome they should not be subjected to hardware removal unless by patient or surgeon preference and noted as medial or lateral hardware removed for preference. On the other hand, if they mention bothersome sensitivity, it would be rated on a 0-5 Likert intensity scale. All bothersome sensation will be subjected to hardware removal and noted as removal for sensitivity. Other reasons for hardware removal indications include infection and non-union or mal-union requiring revision open reduction and internal fixation. The location of symptoms and reason for hardware removal should be specified and documented.

Documentation of Fracture Union

Union will be defined as a pain free fracture site on examination with evidence of radiographic healing and a return to full weight bearing confirmed by the operating surgeon

Power Analysis and Statistics

Retrospective review of ankle hardware removal cases indicates that 6% (8/126) of patients have their hardware removed for non-pain issues (e.g., infection, etc.) at 6 months and 17% (22/126) of patients have their hardware removed for pain on the medial or lateral side of the ankle at 6 months.⁸ Hence, the overall rate of hardware removal is 24% but if we can reduce half of the medial hardware removals the overall rate would be 14.5%. To detect this 9.5% difference, it would take 424 randomized patients (alpha = 0.05, and 80% power). Medial hardware removal will be prohibited for lateral hardware pain.

Utilizing the STRIDE database available at Stanford University, there have been 155 procedures involving fixation of the medial malleolus (CPT: 27766, 27814, 27822, 27823) over the past three years. Assuming a similar procedure burden at the other major Level I Trauma center and extrapolating this three-year data, we estimate the capability to enroll 500 patients over three years.

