All continuous variables will be reported as the mean and errors are reported as standard deviation. All categorical variables will be reported as the subset number and percentage of the total. Comparisons will be performed with the appropriate statistical test when indicated. Statistical significance will be set at p less than 0.05 with an appropriate Bonferroni correction for multiple comparisons when indicated.

Budget

The vast majority of the budget will go toward an experienced fulltime clinical research coordinator, level II (CRCII, Table 2). This person is critical to our success. Appropriately, some funds will be devoted to insuring the proper training and certification for the CRCII involved in this project as well as supply adequate computing power and meet secure data storage needs. Some funds would be used by the principal investigator and co-investigators to offset local travel and travel to national and international meetings to present the findings of this interdisciplinary work, including the American Academy of Orthopaedic Surgeons (AAOS), the Orthopaedic Trauma Association (OTA), and the American Orthopaedic Foot and Ankle Society (AOFAS).

Table 2: General Budget

Expense			Effort	Cost
Personnel	Principal Investigator	[name]	10%	\$36,000/year
	Co-Investigator	[name]	3%	\$10,000/year
	Co-Investigator	[name]	3%	\$10,000/year
	Co-Investigator	[name]	3%	\$10,000/year
	Co-Investigator	[name]	3%	\$10,000/year
	Co-Investigator	[name]	3%	\$10,000/year
	CRCII	TBD: Stanford	100%	\$90,000/year

	CRCII	TBD: 3 rd center	75%	\$68,000/year
	CRCII	TBD: Kaiser	75%	\$68,000/year
Equipment	Computers			\$3,000/year
	Secure Storage			\$1,000/year
Training				\$5,000/year
Travel	Society Meetings			\$5,000/year
	Between Sites			\$5,000/year
				\$275,000/year

Acumed Study Summary	
Company	Stanford University
Title	Prospective, multi-center, randomized, controlled study evaluating the union rate, rate of medial malleolus hardware removal and clinical outcomes after medial malleolus fracture fixation with Acutrak headless compression screws
Short Title	Acutrak Fixation of Medial Malleolus Fractures
Protocol Number	
Treatment Device	Acutrak headless compression screws
Control Device(s)	Mini-fragment Plating, Antiglides Plating, Headed Unicortical Screws, Headed Bicortical Screws, Tension Band Wiring

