Intended Use	The Acutrak headless compression screws are intended to provide fixation and anatomically reduce fractures of the medial malleolus that occur via supination-external rotation, pronation-external rotation, or pronation-abduction resulting in an oblique fracture pattern as well as supination-adduction resulting in a vertical shear fracture pattern.
Study Purpose	The fixation provided by the Acutrak headless compression screws provide sufficient fixation to achieve union and a favorable clinical outcome in both horizontal and vertical medial malleolus fractures when compared to bicortical and unicortical screw fixation, tension band wiring, and mini-fragment or buttress plating. However, minimizing the amount of dissection required for implantation as well as lack of prominent hardware surfaces will reduce the incidence and severity of hardware related pain and correspondingly the necessity of hardware removal.
Study Objectives	
Primary:
 
 • A successful outcome would be a reduction in the rate or severity of hardware related pain localized to the medial malleolus reducing the incidence of hardware removal from the medial malleolus at one year after sustaining an ankle fracture.
	
Secondary:
 
 • Another successful outcome would be an equivalent radiographic and clinical union rate when compared to traditional fixation methods. • Another successful outcome would be an equivalent PROMIS scores when compared to traditional fixation methods.

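### The 424 patients to be randomized are the number needed with a known outcome: the figure has no allowance for loss to follow-up, and the plan states no loss rate

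*Combined protocol and SAP*

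**What the plan says.** All references are to the Combined protocol and SAP.

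- **Power Analysis and Statistics.** The control rate is given as "the overall rate of hardware removal is 24" percent, and "if we can reduce half of the medial hardware removals the overall rate would be 14.5" percent. The size follows: "To detect this 9.5% difference", "it would take 424 randomized patients (alpha = 0.05, and 80% power"). The source figures are removals at 6 months, for non-pain reasons and for pain on either side of the ankle. The next paragraph estimates, from procedure counts, that 500 patients could be enrolled in three years.
- **Study summary, Study Objectives.** The primary objective concerns medial removal "at one year after sustaining an ankle fracture".
- **Follow-up Protocol and Table 1.** Clinic visits are scheduled at 2 weeks, 6 weeks and 3 months. The 6-month, 1-year and 2-year contacts are remote: "The VAS pain scores will be administered telephonically and the PROMIS questionnaires will be mailed to the patients". Table 1 marks hardware removal for recording at every post-operative contact.
- **Statistical methods.** "Statistical significance will be set at p less than 0.05", with a Bonferroni correction where indicated. Neither the sidedness nor a named test is given.
- **Study summary, Number of Subjects.** This row repeats the enrolment capability as over 500 and does not mention 424.

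The plan gives no loss rate, no inflation of the sample size, and no rule for a patient whose removal status is unknown.

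**The concern.** A two-proportion sample size counts patients whose outcome is known. The plan attaches that count to the patients randomized. The two agree only if every randomized patient's removal status is ascertained. Here the primary time point falls in the part of follow-up conducted by telephone and mail, after the last scheduled clinic visit, so some loss should be planned for. If enrolment stopped at 424, any loss would take power below the stated 80%, and a reader of the plan could not tell by how much. With no rule for unknown status, the handling of those patients would also be decided after the data are seen.

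**Working it through.** **Inputs.** Power Analysis and Statistics gives p1 = 0.24, p2 = 0.145, difference 0.095, alpha 0.05 and power 80%. Allocation is not stated, so 1:1 is assumed. Sidedness is not stated, so both are tried. The loss rate d is not stated, so a range is assumed, equal in both arms.

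**Step 1: reproduce 424.** The pooled-variance formula without continuity correction is

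n per arm = [z_a √(2 p̄ q̄) + z_b √(p1 q1 + p2 q2)]² / (p1 − p2)²

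- p̄ = (0.24 + 0.145)/2 = 0.1925, so √(2 × 0.1925 × 0.8075) = 0.5576.
- √(0.24 × 0.76 + 0.145 × 0.855) = √0.306375 = 0.5535.
- One-sided: (1.645 × 0.5576 + 0.8416 × 0.5535)² / 0.095² = 211.9, so 212 per arm and **424** in total. This is an exact match.
- Two-sided: (1.960 × 0.5576 + 0.8416 × 0.5535)² / 0.095² = 269.2, so 270 per arm and 540 in total.

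Because 424 equals the uninflated one-sided result, it contains no allowance for loss.

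**Step 2: power if 424 are randomized and lost patients are dropped.** With n = 212(1 − d) per arm,

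power = Φ{[0.095 √n − z_a × 0.5576] / 0.5535}

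| Assumed loss | With outcome (total) | Power, one-sided 0.05 |
|---|---|---|
| 0% | 424 | 80.0% |
| 5% | 403 | 78.2% |
| 10% | 382 | 76.2% |
| 15% | 360 | 74.1% |
| 20% | 339 | 71.9% |

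Example at 10%: n = 190.8, √n = 13.813, and (1.3122 − 0.9171)/0.5535 = 0.714, so power is 76.2%.

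**Step 3: number to randomize so that 424 have an outcome, 424/(1 − d).** This gives 447, 472, 499 and 530 at 5%, 10%, 15% and 20% loss.

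**Step 4: what the 500 capability would cover.** 1 − 424/500 = 0.152. If 500 were randomized, one-sided power stays at or above 80% up to about 15% loss (82.1% at 10%, 77.9% at 20%).

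**Step 5: separate the sidedness effect.** On a two-sided 0.05 test, 424 gives 70.0% power with no loss at all. That 10-point gap comes from the unstated sidedness. It is not an effect of loss and is not counted in the size of this point.

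**The case against.** The strongest reply is that the plan never says enrolment stops at 424. It says what detection would take, and then estimates that 500 or more could be enrolled. At 500, one-sided power survives about 15% loss, which covers most of the range above. This stands in part: a reader might infer that the trial will miss 80% power, and the documents do not support that, because they fix neither the number to be randomized nor a loss rate. But the 500 is a feasibility estimate that the plan never links to loss. Its basis is also thin: 155 procedures per centre give 2 × 155 = 310 for two centres or 3 × 155 = 465 for the three listed, before eligibility and consent.

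A second reply is that the shortfall is small if follow-up is good. That is correct: at 5% loss it is under 2 points.

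Two other inferences go too far.

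- A reader might conclude that lost patients must be dropped or counted as not removed. The plan commits to no analysis, removal is recorded at each contact, a removal seen before loss stays known, and a missed one-year call might be recovered at two years. Dropping lost patients is used above only as a simple benchmark.
- A reader might take 424 to mean patients with known one-year medial-removal status. The rates behind it are 6-month, overall removal rates that include non-pain and lateral removals, so that label would attach the figure to an endpoint it was not computed for.

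**Conclusion.** The point holds in a limited form. The 424 is the uninflated one-sided number with a known outcome, labelled as the number to randomize, and the plan makes no declared allowance for loss. This is an omitted design allowance; the formula itself was evaluated correctly. If 424 are randomized and lost patients are dropped, one-sided power falls by about 2 points at 5% loss, 4 at 10%, 6 at 15% and 8 at 20%. These sizes rest on assumed loss rates, equal loss in both arms, 1:1 allocation, the plan's own rates of 24% and 14.5%, and the one-sided test that reproduces 424. Whether the trial would actually fall short cannot be settled from the documents. The unstated sidedness is a separate and larger issue, and it should be resolved first because the restated power depends on it.

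**What to change.** Without enrolling more patients:

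1. State whether the 0.05 test is one-sided or two-sided.
2. Relabel 424 as the number of patients with a known hardware-removal outcome, on the rates actually used (overall removal, 6-month source figures).
3. State the planned number to be randomized and an assumed loss rate, and give power at 5% to 20% loss on the stated sidedness. If the 500 is meant as the target, say so and say that it includes an allowance for loss.
4. Record the date of each removal. Analyse medial removal by one year as time from surgery to removal, with the Kaplan-Meier difference at one year and a log-rank test, censoring at last contact. Patients lost early then contribute the time for which they were observed.
5. Pre-specify a sensitivity analysis for patients with unknown one-year status, since censoring assumes that loss is unrelated to removal.

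The cost is revised wording, one date field added to data already collected at each contact, and a less favourable power statement. Should the sponsor prefer to inflate instead, the one-sided numbers to randomize are those in Step 3 of the working.

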Number of Subjects	Utilizing the STRIDE database available at Stanford University, there have been 155 procedures involving fixation of the medial malleolus (CPT: 27766, 27814, 27822, 27823) over the past three years. Assuming a similar procedure burden at another major Level I Trauma center at Kaiser Permanente Hospital, South Sacramento and extrapolating this three-year data, we estimate the capability to enroll and randomize over 500 patients requiring medial malleolus fixation over three years between the three centers.
Number of Sites	Three Level I Trauma Centers will participate: 
 • Stanford Hospital and Clinics • Kaiser Permanente – South Sacramento • Brigham and Women's Hospital- Boston
Procedure Schedule	See Table 1
Subject Duration	The estimated duration for each subject is 2 years. Subjects are released from postoperative follow-up after post-operative observation for two years.
Study Duration	The estimated duration of the study is 5 years: 3 years for enrollment and 2 year for postoperative follow-up for each enrolled subject.
Safety	All adverse events and complications will be continuously monitored throughout the study. The type and frequency will be analyzed by a medical monitor.
Statistical Methods	All continuous variables will be reported as the mean and errors are reported as standard deviation. All categorical variables will be reported as the subset number and percentage of the total. Comparisons will be performed with the appropriate statistical test when indicated. Statistical significance will be set at p less than 0.05 with an appropriate Bonferroni correction for multiple comparisons when indicated.

References

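### The stated capacity of 500 patients in three years does not follow from the protocol's own counts, which give 310 procedures at two centres and no figure for the third

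*Combined protocol and SAP*

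**What the plan says.** Under Power Analysis and Statistics, the protocol sets the sample size at 424 randomised patients (24% versus 14.5% hardware removal, alpha 0.05, 80% power). It then turns to feasibility. A Stanford database search by procedure code shows that "there have been 155 procedures involving fixation of the medial malleolus" over three years. The text continues "Assuming a similar procedure burden at the other major Level I Trauma center" and concludes "we estimate the capability to enroll 500 patients over three years".

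The Acumed Study Summary repeats the argument under Number of Subjects. The similarity assumption is again attached to one further site: "Assuming a similar procedure burden at another major Level I Trauma center at Kaiser Permanente Hospital, South Sacramento". The conclusion is now larger and credited to more sites: "we estimate the capability to enroll and randomize over 500 patients requiring medial malleolus fixation over three years between the three centers". Number of Sites states "Three Level I Trauma Centers will participate" and adds a Boston hospital, with no procedure volume. The budget in Table 2 carries a coordinator line for "TBD: 3 rd center". The Institutional Review Board and HIPAA section and the Randomization section name only Stanford and Kaiser – South Sacramento.

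Study Duration states "The estimated duration of the study is 5 years: 3 years for enrollment", followed by two years of follow-up.

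**The concern.** The 500 is presented as an extrapolation from a count and a stated assumption, yet those inputs do not produce it. One centre at 155 plus one similar centre is 310. Three centres could yield more, but the third centre's contribution is neither counted nor assumed anywhere.

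The figure matters because it is the only support for recruiting 424 patients within three years and finishing in five. If it is too high, either enrolment closes short of 424 and power falls below plan, or enrolment continues and the study overruns its stated duration.

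**Working it through.** **Inputs from the documents**
- Stanford volume: 155 procedures in 3 years (Power Analysis and Statistics).
- Second centre: assumed similar, so 155 (same section; Number of Subjects).
- Third centre: no volume given.
- Target: 424 randomised. Rates: 24% versus 14.5%. Alpha 0.05, sidedness not stated. Power 80%.
- Enrolment 3 years, follow-up 2 years (Study Duration).

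**Assumptions made here**
- 1:1 allocation.
- Where a third centre is included, it also performs 155 procedures in 3 years.
- Share of procedures enrolled: 60%, range 50–80%. The documents give none.

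**1. Trying to reproduce 500**
- Two centres: 155 × 2 = 310, and 500 / 310 = 161%.
- Three equal centres: 155 × 3 = 465, and 500 / 465 = 107.5%.

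Neither gives 500. With every procedure enrolled at all sites, the third centre would need 500 − 310 = 190 procedures, or 190 / 155 = 1.23 times Stanford's volume.

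**2. Comparing 424 with the counts**
- 424 / 310 = 137%, so the target exceeds every procedure at the two quantified centres.
- 424 / 465 = 91% of all procedures at three equal centres.
- With full enrolment, the third centre would need 424 − 310 = 114 procedures (0.74 × 155).
- With enrolment share f at all sites, it would need 424/f − 310: 538 at 50%, 397 at 60%, 220 at 80%.

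**3. Time to 424 at three equal centres**

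Yearly accrual is 465 × f / 3 = 155 × f, so the enrolment time is 424 / (155 × f).

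| f | Patients in 3 years | Years to enrol 424 | Plus 2 years of follow-up |
|---|---|---|---|
| 50% | 233 | 5.5 | 7.5 |
| 60% | 279 | 4.6 | 6.6 |
| 80% | 372 | 3.4 | 5.4 |
| 100% | 465 | 2.7 | 4.7 |

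**4. Power if enrolment stopped at three years**

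The pooled-variance formula for two proportions, per arm, is

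n = [z_α √(2p̄(1−p̄)) + z_β √(p₁(1−p₁) + p₂(1−p₂))]² / (p₁ − p₂)²

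with p₁ = 0.24, p₂ = 0.145 and p̄ = 0.1925. One-sided alpha 0.05 gives 211.9, so 212 per arm and 424 in total, which is the plan's own figure. Two-sided 0.05 gives 269.2, so 270 per arm and 540 in total. Both bases are shown below because the plan does not name one. That gap is a separate matter and is not a recruitment effect.

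| N | Source | Power, one-sided | Power, two-sided |
|---|---|---|---|
| 424 | target | 80% | 70% |
| 465 | three equal centres, all enrolled | 83% | 74% |
| 372 | three equal centres, 80% | 75% | 64% |
| 310 | two centres, all enrolled | 68% | 56% |
| 279 | three equal centres, 60% | 64% | 52% |
| 233 | three equal centres, 50% | 58% | 45% |

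**The case against.** The strongest reply is that three sites are plainly intended, so 465 is the fair benchmark. On that reading 500 is only 7.5% high, 424 lies within the procedure count, and the comparisons with 310 describe a study in which the third centre contributes nothing. The figure is also offered as an estimate, and a third centre with 190 procedures would produce it at full enrolment. Three centres are indeed the better reading, and the capacity is unsupported rather than proved impossible. But 465 rests on an assumption the protocol never makes, the summary claims more than 500, and reaching 424 would still require 91% of all procedures to be enrolled.

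Three further points stand as limits:
- The enrolment fractions are scenarios chosen here, so the totals and durations built on them illustrate the risk and do not measure the protocol's error.
- The protocol does not say whether the 155 was screened against its eligibility criteria, so some exclusions may already be out. Refusals and missed cases cannot be.
- Power is lost only if enrolment closes early. The duration is described as an estimate, and continuing to 424 preserves the planned power at the cost of time. The primary objective is at one year, so at 60% enrolment the primary data would be complete at about 4.6 + 1 = 5.6 years, with 6.6 years for full follow-up.

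**Conclusion.** The concern holds. The stated 500 cannot be derived from the figures given: they support 310 procedures, half of them assumed, or 465 if an equal third centre is added by assumption. Recruiting 424 in three years is therefore not shown to be feasible. It is out of reach with the two quantified centres, and with three equal centres it needs 91% of procedures enrolled. How far recruitment would actually fall short depends on the third centre's volume and the enrolment fraction, neither of which is in the documents. The point concerns feasibility, duration and possibly power. It does not affect bias or the type I error rate.

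**What to change.** Replace the 500 statements in Power Analysis and Statistics and in Number of Subjects with a derivation along these lines:

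> Stanford recorded 155 procedures in three years; assuming a similar number at Kaiser – South Sacramento gives 310. The third centre recorded [count], for a total of [x] (465 if assumed equal), before exclusions and refusals. At an enrolment fraction of [f]% we expect [n] patients in three years.

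Then do one of two things: restate the enrolment period and study duration needed for 424, or state the power at the number reachable in three years, naming the sidedness used. Bring the site lists in the Institutional Review Board and HIPAA section and the Randomization section into line with the three sites in the summary and budget.

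The change requires rewording, one procedure count from the third centre, and a reasoned enrolment fraction, for which the documents hold no data. The stated capacity, duration or power will look less favourable. A longer enrolment period would also extend a budget that is set per year.

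### The 424 patients are sized on one removal comparison at an undivided 0.05; if that test enters the plan's undefined Bonferroni split, the stated 80% power is not delivered

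*Combined protocol and SAP*

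**What the plan says.** Power Analysis and Statistics bases the sample size on one comparison: "the overall rate of hardware removal is 24% but if we can reduce half of the medial hardware removals the overall rate would be 14.5" percent. It continues "To detect this 9.5% difference", "it would take 424 randomized patients (alpha = 0.05, and 80% power". It does not say whether the test is one- or two-sided.

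The multiplicity rule stands at the end of the same section and again under Statistical Methods in the study summary. Both set significance at p below 0.05 "with an appropriate Bonferroni correction for multiple comparisons when indicated". Neither place says which comparisons form the family, what the divisor is, or whether the removal test is included.

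Specific Aims lists four unranked aims: equivalence on union, equivalence on PROMIS, superiority on hardware-related pain and superiority on hardware removal. In the study summary, Study Objectives labels union and PROMIS secondary. The one primary objective there is "a reduction in the rate or severity of hardware related pain localized to the medial malleolus", tied in the same sentence to a lower incidence of medial hardware removal at one year. The summary then relists all four aims, again unranked, under Safety Objective.

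**The concern.** The sample size and the multiplicity rule were not written against the same alpha. The sample size gives the removal test all of 0.05. The analysis text allows that 0.05 to be divided on a condition it does not define, and the primary objective contains pain as well as removal, so a split over those two superiority aims is a natural reading.

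Two things are at stake. If the removal test is corrected, the trial is underpowered against its own claim. If it is not, nothing in the text fixes that decision in advance, so it can be taken once the p-values are known. A removal result with p between 0.025 and 0.05 would be significant under one choice and not under the other.

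**Working it through.** **Inputs from Power Analysis and Statistics.** Rates of 24% and 14.5%, difference 0.095, alpha 0.05, power 80%, total 424. **Assumptions, because the documents are silent.** 1:1 allocation (212 per arm), no dropout, no continuity correction.

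**Formulas (pooled variance under the null).** With p̄ = (p1 + p2)/2, A = √[2p̄(1 − p̄)] and B = √[p1(1 − p1) + p2(1 − p2)]:
- n per arm = [(z_α·A + z_power·B)/(p1 − p2)]²
- power = Φ{[(p1 − p2)√n − z_α·A]/B}

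**Step 1: reproduce 424 from the printed rates.** p̄ = 0.1925, A = 0.5576, B = 0.5535.
- One-sided 0.05 (z = 1.645): n = [(1.645 × 0.5576 + 0.8416 × 0.5535)/0.095]² = 211.9, so 212 per arm and 424 in total. This matches exactly.
- Two-sided 0.05 (z = 1.960): n = 269.2, so 270 per arm and 540 in total.

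**Step 2: power at 212 per arm on the printed rates.** (p1 − p2)√n = 0.095 × √212 = 1.3832.
- One-sided 0.05: (1.3832 − 1.645 × 0.5576)/0.5535 = 0.842, power 80.0%.
- Two-sided 0.05: (1.3832 − 1.960 × 0.5576)/0.5535 = 0.525, power 70.0%.
- Two-sided 0.025: (1.3832 − 2.241 × 0.5576)/0.5535 = 0.241, power 59.5%.

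**Step 3: the other basis that gives 424.** The plan attributes the 9.5-point fall to halving medial removals. That implies medial removal of 2 × 9.5% = 19% against 9.5%. The plan does not print these rates. p̄ = 0.1425, A = 0.4944, B = 0.4898.
- Two-sided 0.05: n = [(1.960 × 0.4944 + 0.8416 × 0.4898)/0.095]² = 211.4, so 212 per arm and 424 in total. This also matches exactly.
- Power at 212 per arm, two-sided 0.05: (1.3832 − 1.960 × 0.4944)/0.4898 = 0.846, power 80.1%.
- Two-sided 0.025: (1.3832 − 2.241 × 0.4944)/0.4898 = 0.562, power 71.3%.

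**Summary at N = 424**

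| Rates | Sidedness | Alpha undivided | Split over two |
|---|---|---|---|
| 24% vs 14.5% (printed) | one-sided | 80.0% | 70.0% |
| 24% vs 14.5% (printed) | two-sided | 70.0% | 59.5% |
| 19% vs 9.5% (implied) | two-sided | 80.1% | 71.3% |

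On every row, a split over two costs 9 to 10 percentage points of power.

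**The case against.** The strongest reply is that the plan breaks no rule of its own. The correction is conditional and has no divisor. One primary removal test at the full 0.05, with correction kept for the secondary comparisons, fits the text and leaves primary power untouched. This stands, so the loss of power is conditional.

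Four stronger readings are tempting, and the documents do not support them.

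- **Bonferroni covers all four aims, so power is 49%.** That figure is correct arithmetic for two-sided 0.0125 on the printed rates. But no passage applies the correction over four aims, and Study Objectives labels union and PROMIS secondary. It also adds an undeclared two-sided test to an undeclared divisor.
- **The primary objective offers pain or removal as alternative successes.** The conjunction joins rate and severity of pain. The sentence goes on to present less pain as the route to fewer medial removals. It is compound, but it does not define separate co-primary tests.
- **The 424 can only be one-sided.** This holds for the printed overall rates. The implied medial rates give 424 two-sided. Against that basis, 19% is not stated and exceeds the 17% removed for pain on either side in the cited review.
- **Without correction, family-wise error is 9.8% for two tests or 18.5% for four.** These are 1 − 0.95² and 1 − 0.95⁴ and assume independence. Criteria for Removal of Hardware ties bothersome sensation to removal, so pain and removal should be correlated. For two two-sided tests, an illustrative correlation of 0.7 gives 8.3% and 0.9 gives 7.0%. The four-test figure also counts two equivalence aims that are labelled secondary.

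**Conclusion.** The point holds in conditional form. The sample size assumes an undivided 0.05 for removal, and the analysis text does not guarantee it. If removal shares alpha with one other test, power at 424 is 70% (one-sided) or 60% (two-sided) on the printed rates, or 71% (two-sided) on the implied medial rates.

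Separately from any correction, the printed rates give 80% only one-sided, and the plan never declares a one-sided test. If those rates are kept and the test is two-sided, power is 70% before any split.

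A reader might infer that the plan's own rule already defeats its stated power, or that its family-wise error is shown to exceed 5%. Neither is established, because the family is undefined and removal may be meant as the sole primary test.

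The figures rest on 1:1 allocation, no dropout and the pooled normal approximation. The plan's source rates are six-month figures and its arithmetic starts from overall removal, whereas the primary objective is medial removal at one year. Power for that endpoint therefore needs rates the documents do not give.

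**What to change.** 1. Name medial hardware removal at one year as the single primary endpoint, tested at the full two-sided 0.05 with no correction.
2. Replace the Bonferroni sentence, in both places where it appears, with Holm across the three remaining aims: medial pain, union equivalence and PROMIS equivalence. Holm compares the ordered p-values with 0.05/3, 0.05/2 and 0.05, where Bonferroni holds all three to 0.05/3 = 0.0167. It is never less powerful. State whether this step is open only after the primary test succeeds. If it is not, the 5% level applies to the primary test and to the secondary family separately. The two equivalence tests also need margins, which the plan does not give.
3. A pre-specified fixed order is an alternative to Holm. Its downside is that nothing after a failed test can be claimed. Union appears under Safety Objective, so it should not be placed behind pain without a stated reason.
4. Restate power at 424 for the named endpoint, giving the rates and sidedness used. If the printed 24% versus 14.5% is kept, the two-sided figure is 70%. If medial rates were meant, print and justify them.

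The cost is wording, settled before any comparative data are seen. No increase in enrolment is required for this fix. Restoring 80% two-sided on the printed rates would be a separate decision: it needs 540 patients, above the enrolment estimate of 500, at which two-sided power is 77%.
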